#### 11.4.3.1.3 Cogstate Identification Test

The Cogstate Identification Test is a computerized measure of visual attention and uses a validated choice RT paradigm with playing card-like stimuli displayed on a computer screen. In this test, the playing cards are all either red or black. The patient is asked whether the card displayed in the center of the screen is red. The patient responds by pressing the “yes” key when the card is red and “no” when it is black. The software measures the speed and accuracy of each response. The main outcome measure for the test is speed of performance (mean of the log10-transformed RTs for correct responses). Decreasing scores represent improved test performance.

Early termination visits will be summarized and analyzed under Week 11 (see [section 9.2](#) for details on the visit window) regardless of the discontinuation reason.

The same summaries and analyses as performed for Cogstate detection test will be repeated for the Cogstate identification test endpoint. Further details on the summaries and inferential analyses are provided in [section 11.4.3.1.2](#).

The analysis of the Identification Test will be performed by Cogstate; more details are provided in the Cogstate SAP.

#### 11.4.3.1.4 Cogstate One Back Test

The Cogstate One Back Test is a computerized measure of working memory and uses a validated n-back paradigm with playing card stimuli displayed on a screen. The patient is asked whether the card displayed in the center of the screen is the same as the card presented immediately previously. The patient responds

---

by pressing the “yes” or “no” key. The software measures the speed and accuracy of each response (mean of the log10-transformed RTs for correct responses). Decreasing scores represent improved test performance.

Early termination visits will be summarized and analyzed under Week 11 (see [section 9.2](#) for details on the visit window) regardless of the discontinuation reason.

The same summaries and analyses as performed for Cogstate detection test will be repeated for the Cogstate on back test endpoint. Further details on the summaries and inferential analyses are provided in [section 11.4.3.1.2](#).

The analysis of the One Back Test will be performed by Cogstate; more details are provided in the Cogstate SAP.

#### 11.4.3.1.5 Myotonic Dystrophy Health Index (MDHI)

The MDHI is a disease-specific, patient-reported outcome measure for DM1. It focuses on the major symptoms experienced by patients with DM1. The tool consists of multiple symptom-related questions grouped into several themes including fatigue, sleep, and cognitive impairment.

Subscales of the MDHI measure patients' perception of their health as it relates to mobility, upper extremity function, ability to do activities, fatigue, pain, gastrointestinal issues, vision, communication, sleep, emotional issues, cognitive impairment, social satisfaction, social performance, myotonia, breathing, swallowing, and hearing.

Each subscale score is a weighted average of its components; the prevalence of each symptom and theme (prevalence scores), and their importance to patients (impact scores) form the basis of the weights. The total score is a weighted average of the subscales where the weights are based on the population impact scores. The subscales and total scores have been validated independently ([Heatwole et al 2014](#) and [Heatwole et al 2016](#)), and are scored on a scale of 0-100, with a higher score representing a higher burden of disease.

The questionnaires will be scored centrally (University of Rochester, Rochester, NY) and the total score and sub-scores will be provided for analysis.

Early termination visits will be summarized and analyzed under Week 7 or Week 11 (depending on which visit they are closest to, see [section 9.2](#) on visit window) regardless of the discontinuation reason.

A descriptive summary of the MDHI total score, the fatigue sub-score, the sleep sub-score, and the cognitive impairment sub-score of the absolute values and change from Baseline to Week 7 and to Week 11 will be reported by treatment group and for the active groups combined.

The change from Baseline MDHI total score will be analyzed using a Mixed Model Repeated Measures (MMRM) approach. Fixed effects will be included for treatment, visit, treatment\*visit interaction, baseline value, and wake-promoting agents stratification factor. An unstructured covariance structure will be utilized.; in case of failure to converge, covariance structures TOEPH (Heterogeneous Toeplitz), ARH(1) (Heterogeneous auto-regressive 1), and VC (Variance Components) will be tested in the order specified. Least Square means, standard errors, and the LS mean differences (each treatment versus placebo and the pooled active groups versus placebo) at each visit will be reported. All estimates will be generated from a single model, i.e., the pooled active estimates will be created via model contrasts.

#### 11.4.3.1.6 Epworth Sleepiness Scale (ESS)

The ESS is a questionnaire with eight questions in which respondents are asked to rate, on a 4-point scale (0-3), their usual chances of dozing or falling asleep while engaged in eight different activities. The questionnaire is a validated measure with high specificity and sensitivity for assessing subjective sleepiness in narcolepsy ([Johns 1991](#)).

The total ESS score (sum of 8 item scores) can range from 0 to 24; the total score gives an estimate of the person's 'average sleep propensity' (ASP), across a wide range of activities in their daily lives. The higher

the ESS score, the higher that person's ASP in daily life or their 'daytime sleepiness' (Hirshkowitz 2017). If one or more item's score is missing, the ESS score will be invalid and not be derived.

- 0-5: Lower Normal Daytime Sleepiness
- 6-10: Higher Normal Daytime Sleepiness
- 11-12: Mild Excessive Daytime Sleepiness
- 13-15: Moderate Excessive Daytime Sleepiness
- 16-24: Severe Excessive Daytime Sleepiness

A descriptive summary of ESS for the absolute values and change from Baseline to Week 7 and to Week 11 will be reported by treatment group and for the active groups combined. In addition, frequency count and percentage of the ESS score at each visit versus Baseline category will be provided by way of shift tables. Early termination visits will be summarized under Week 7 or Week 11 (depending on which visit they are closest to, see section 9.2 on visit window) regardless of the discontinuation reason.

The change from Baseline will be analyzed using a Mixed Model Repeated Measures (MMRM) approach. Fixed effects will be included for treatment, visit, treatment\*visit interaction, baseline value, and wake-promoting agents stratification factor. An unstructured covariance structure will be utilized.; in case of failure to converge, covariance structures TOEPH (Heterogeneous Toeplitz), ARH(1) (Heterogeneous autoregressive 1), and VC (Variance Components) will be tested in the order specified. Least Square means, standard errors, and the LS mean differences (each treatment versus placebo and the pooled active groups versus placebo) at each visit will be reported. All estimates will be generated from a single model, i.e., the pooled active estimates will be created via model contrasts.

#### 11.4.3.1.7 Clinical Global Impression of Severity (CGI-S) of Excessive Daytime Sleepiness (EDS)

Numerical values in parentheses were assigned in the datasets. Early termination visits will be summarized and analyzed under Week 7 or Week 11 (depending on which visit they are closest to, see section 9.2 on visit window) regardless of the discontinuation reason.

A descriptive summary of CGI-S for the absolute values and change from Baseline to Week 7 and to Week 11 will be presented by treatment group and for the active groups combined. In addition, frequency count and percentage of the CGI-S score at each visit versus baseline category will be provided using a shift table.

The change from Baseline will be analyzed using a Mixed Model Repeated Measures (MMRM) approach. Fixed effects will be included for treatment, visit, treatment\*visit interaction, baseline value, and wake-promoting agents stratification factor. An unstructured covariance structure will be utilized; in case of failure to converge, covariance structures TOEPH (Heterogeneous Toeplitz), ARH(1) (Heterogeneous autoregressive 1), and VC (Variance Components) will be tested in the order specified. Least Square means, standard errors, and the LS mean differences (each treatment versus placebo and the pooled active groups versus placebo) at each visit will be reported. All estimates will be generated from a single model, i.e., the pooled active estimates will be created via model contrasts.

---

#### 11.4.3.1.8 Patient Global Impression of Severity (PGI-S) of Excessive Daytime Sleepiness (EDS)

---

---

- [REDACTED]
- [REDACTED]
- [REDACTED]
- [REDACTED]

Numerical values in parentheses were assigned in the datasets. The same summaries and analyses performed for CGI-S will be repeated for the PGI-S endpoint. Further details on the summaries and inferential analyses are provided in [section 11.4.3.1.7](#).

#### 11.4.3.1.9 Mean Sleep Latency

The MWT, a daytime polysomnographic procedure for the evaluation of daytime somnolence/wakefulness, is used to assess an individual's ability to stay awake while resisting the pressure to fall asleep. The MWT evaluates the magnitude of sleepiness in relationship to the underlying wakefulness system's functioning.

For the MWT, patients will be administered four 40-minute sessions at 2-hour intervals according to the validated standard ([Doghramji et al 1997](#)), with the initial session beginning two hours after waking.

The session will end if the patient falls asleep, or if more than 40 minutes elapse without the patient falling asleep. The sleep latency, or the time it takes to fall asleep, will be recorded.

Analysis of the MWT will be based on the average MSL computed from the four sessions.

A descriptive summary of MSL for the absolute values and change from Baseline to Visit 5 will be reported by treatment group and for the active groups combined. If the termination visit occurs after the Visit4 Double-Blind visit, the early termination data will be windowed to Visit 5 regardless of the discontinuation reason.

The change from Baseline to Visit 5 will be analyzed using an ANCOVA model with fixed effect terms for treatment, baseline value, and wake-promoting agents stratification factor. Least Square means, standard errors, and the LS mean differences (each treatment versus placebo and the pooled active groups versus placebo) will be reported. All estimates will be generated from a single model, i.e., the pooled active estimates will be created via model contrasts.

#### 11.4.3.1.10 Sustained Attention to Response Task (SART)

The SART is a measure of sustained attention, which is the ability to focus on an activity or stimulus over a long period of time, or to direct focus and cognitive ability on specific stimuli. It is a computer-based go/no-go task that requires participants to withhold behavioral response to a single, infrequent target presented amongst a background of frequent non-targets. Both accuracy and response speed, quantified as response time, are important. The total, go, and no-go scores will be summarized and analyzed. The total score is the sum of the go score and no-go score.

Early termination visits will be summarized and analyzed under Visit 5 (see [section 9.2](#)) regardless of the discontinuation reason. The actual values and change from Baseline of the go, no-go and total score will be summarized using descriptive statistics.

In addition, it is assumed that the change from Baseline in SART parameters are not normally distributed. For the difference between lower dose pitolisant and placebo, the difference between higher dose pitolisant and placebo, and the difference between pooled pitolisant and placebo, p-values will be generated and reported. Early termination visits will be summarized and analyzed under Visit 5 regardless of the discontinuation status.

---

### 11.4.4 Open-Label Extension Efficacy Analyses

The OLE efficacy parameters are:

- DSS
- ESS
- FSS
- Cogstate (Detection Test, Identification Test, One Back Test)
- MDHI Total score and sub-scores of sleep, fatigue and cognitive impairment
- CGI-S for EDS
- PGI-S for EDS

Actual and change from Baseline results in the OLE Phase will be summarized by using descriptive statistics at each open-label visit. Results will be tabulated by total. In addition, shift tables from baseline to each of the OLE visits will be provided for DSS, ESS, CGI-S and PGI-S.

### 11.5 PK Analyses

Concentration-time data of pitolisant and BP1.3484 will be summarized using descriptive statistics (number of observations, number of results less than the lower limit of quantification, SD, geometric mean, geometric SD, coefficient of variation [%], median, minimum, and maximum) based on the PK population in the Double-Blind Treatment Phase by randomized treatment group (lower dose and higher dose only). For summarization, plasma concentrations below the quantifiable limit (BLQ) will be set to zero.

Concentration will be listed.

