## 6.4. Pharmacokinetic Assessments

Blood samples for determination of pitolisant and its major metabolite concentrations (trough and at the time of maximum concentration  $[t_{max} (3 \text{ hours } \pm 30 \text{ minutes post dose})])$  will be collected during the Stable Dose Period of the Double-Blind Treatment Phase (Visits 3 and 5), as detailed in Section 7.2.4.1 and Section 7.2.4.4, respectively. Triplicate 12-lead ECGs will be performed before each PK sample collection. At Visit 3, the Holter monitor should be placed on the patient and continuous recording started as the 12-lead ECG (in triplicate) data are taken from the Holter monitor recording. The estimated total volume of blood to be drawn on PK sampling days, including samples for PK analyses (4.0 mL per sample), serum chemistry tests (5.0 mL per sample), and hematology tests (4.0 mL per sample) is presented in Table 9. The total volume of blood collected is not to exceed the maximal allowable for adults of 10.5 mL/kg or 550 mL, whichever is smaller, over any 8-week period (NIH 2009).

Detailed instructions on PK sample collection, processing, storage, and shipping procedures are provided in the Laboratory Manual.

	Blood Sample Volume (mL)			
Visit	РК	Serum Chemistry	Hematology	Total
Visit 3 (Day 22 ±3 days)	4	5	4	13
Visit 5 (Day 77 ±3 days)	4	5	4	13

 Table 9:
 Estimated Total Blood Draw Volumes on Pharmacokinetic Sampling Days

PK = pharmacokinetics

Note: Serum chemistry and hematology parameters are listed in Table 8.

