## 8 Study Design

### 8.1 General Design

This is a randomized, Double-Blind, placebo-controlled, parallel-group study in adult patients (ages 18 to 65 years) with DM1, followed by an optional OLE Phase.

The study will consist of a Screening Period (up to 45 days), an 11-week Double-Blind Treatment Phase (including a 3-week Titration Period and an 8-week Stable Dose Period), and an optional OLE Phase. The OLE Phase will continue until Day 459/Month 15/Visit 8 for each patient, unless the patient withdraws from the study early or the Sponsor elects to terminate the study. An overall schema of the study design is provided in [Figure 1](#).

After Screening, approximately 30 patients ages 18 to 65 years who meet all eligibility criteria will be randomized at the Baseline Visit in a 1:1:1 ratio to lower dose pitolisant (17.8 mg), higher dose pitolisant (35.6 mg), or matching placebo. In the Double-Blind Treatment Phase, patients will be titrated to their randomized stable dose of study drug during the 3-week Titration Period ([Table 1](#)). After completion of the 3-week Titration Period, patients will continue to take study drug at their randomized dose once daily in the morning upon waking for an additional 8 weeks of blinded treatment (Stable Dose Period). The duration of the Double-Blind Treatment Phase will be 11 weeks. Adjustments to study drug dosing outside of the protocol-specified titration schedule are not allowed during the 11-week Double-Blind Treatment Phase.

Following the 11-week Double-Blind Treatment Phase, eligible patients will be given the opportunity to participate in an optional OLE Phase. During the OLE Phase, all eligible patients will receive treatment with open-label pitolisant and will be titrated during a 3-week Titration Period to a dose of 35.6 mg (or a maximum dose up to 35.6 mg based on Investigator assessment of tolerability) ([Table 2](#)). Adjustments to pitolisant dose are permitted during the OLE Phase; pitolisant dose can be adjusted (higher or lower) based on Investigator assessment of tolerability; the maximum dose allowed is 35.6 mg once daily.

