## 10.4 Pharmacokinetic Population

The PK population will include all patients who received at least one dose of study drug and have calculable concentrations of pitolisant available for analysis.

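### SAP 11.5 sets BLQ concentrations to zero with no exception for the geometric mean and geometric SD, so both break down in any PK summary cell that contains a BLQ value

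*SAP*

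**What the plan says.** SAP 11.5 lists the statistics for the concentrations of pitolisant and its metabolite BP1.3484: the number of observations, then "number of results less than the lower limit of quantification, SD, geometric mean, geometric SD, coefficient of variation [%], median, minimum, and maximum". The handling rule follows: "plasma concentrations below the quantifiable limit (BLQ) will be set to zero". It is worded for the summaries as a whole, with no exception for the geometric statistics. The tables use the PK population and show the two active arms as randomized.

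No other section supplies an exception:

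- SAP 10.4 admits dosed patients who "have calculable concentrations of pitolisant available for analysis". This is a condition on the patient. Someone with one quantifiable sample is in the population, and any BLQ samples from that person stay in the data.
- SAP 11 sets the general conventions for continuous data and is silent on BLQ values and geometric statistics.
- Protocol 9.4.4 promises descriptive statistics and no more.

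Protocol 6.4 and SAP Table 6 fix the sampling: pre-dose and 3 hours post-dose, at Visits 3 and 5.

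**The concern.** A geometric mean and geometric SD are computed from logarithms, and zero has no logarithm. A rule that puts zeros into the data cannot serve these two statistics once a BLQ value is present. The programmer would then have to choose: print 0, print that the value is not calculable, drop the record, or substitute some positive number. The SAP does not say which, and the choices give materially different results.

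The trough and 3-hour concentrations are the only PK results planned, and the arms are small, so a single BLQ value decides what a cell shows. The choice should be made while the SAP is being finalized, before unblinding, and not when the tables are programmed.

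**Working it through.** The plan states no figure on this point, so there is nothing to reproduce.

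**1. Cells.** Two active arms × two visits × two time points × two analytes = 16 summary cells. SAP 8.1 plans about 30 patients randomized 1:1:1, so each cell holds at most about 30/3 = 10 patients.

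**2. Definitions.** For values x₁ … xₙ:

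- geometric mean = (x₁ × … × xₙ)^(1/n) = exp(mean of ln xᵢ)
- geometric SD = exp(SD of ln xᵢ)

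If one xᵢ is 0, the product is 0 and the geometric mean is 0. Since ln 0 does not exist, the SD of the logs does not exist either, and the geometric SD is undefined. This is true whatever the other values are and needs no assumption.

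**3. How far the possible remedies diverge.** For illustration only, ten values were drawn from an assumed log-normal distribution (median 20, log-SD 0.5): 23.8, 30.2, 23.6, 10.4, 31.5, 25.0, 15.3, 26.7, 24.0, 23.2. The lowest (10.4) is then replaced by a BLQ result. The LLOQs are assumed, because the documents give none.

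| Handling | n used | Geometric mean | Geometric SD |
|---|---|---|---|
| Before replacement, no BLQ | 10 | 22.4 | 1.39 |
| BLQ = 0, as SAP 11.5 says | 10 | 0 | undefined |
| BLQ excluded | 9 | 24.4 | 1.23 |
| BLQ = LLOQ/2, LLOQ 0.1 | 10 | 13.1 | 7.15 |
| BLQ = LLOQ/2, LLOQ 0.5 | 10 | 15.4 | 4.31 |
| BLQ = LLOQ/2, LLOQ 1.0 | 10 | 16.5 | 3.47 |

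Exclusion and substitution both give finite answers, but they are far apart, so the rule has to be fixed in advance.

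**4. Chance that a cell is affected.** With per-sample BLQ probability p and independent patients, P(at least one BLQ in 10) = 1 − (1 − p)^10. The values of p are assumptions.

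| p | P(at least one BLQ) |
|---|---|
| 1% | 1 − 0.99^10 = 9.6% |
| 2% | 1 − 0.98^10 = 18.3% |
| 5% | 1 − 0.95^10 = 40.1% |
| 10% | 1 − 0.90^10 = 65.1% |

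**The case against.** The strongest defence is that the SAP is underspecified for one case and not contradictory. Without a BLQ value every listed statistic can be computed. With one, the geometric mean is still a number (0), and the median, minimum, maximum, SD and CV% survive. PK is not among the study objectives or endpoints, the tables are descriptive, and no decision hangs on them. All of that stands, and it limits the scope. It does not rescue the geometric SD, which has no value under the stated rule. Nor is the SAP silent here: it gives a rule for all summaries, and that rule fails for two of the statistics it covers.

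A reader might infer more than the documents support:

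- *That data would be lost unannounced.* The number of observations and the BLQ count are both reported, and all concentrations are listed. If zeros were dropped, the n used could be recovered by subtraction. What the reader would lack is a statement that this is what was done.
- *That BLQ values are expected, most likely from a missed dose before a trough.* Planning a count is not a forecast. The documents give no LLOQ, no half-life for pitolisant and no expected trough concentration, so neither frequency nor source can be determined.
- *That the arithmetic mean was deliberately left out beside SD and CV%.* SAP 11 and Protocol 9.1 both list the mean for continuous data. The omission in 11.5 reads as a slip.
- *That grouping by randomized arm is an error.* It is an explicit choice. Titration is fixed, and all patients are to be at their randomized dose by Day 15, before the first PK sample at Day 22. The grouping would matter only if mis-dosing occurred, and nothing in the documents shows that it did.

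**Conclusion.** The point holds in limited form. SAP 11.5 is wrong as written for the geometric mean and geometric SD in any of the 16 cells with at least one BLQ value. There the stated rule yields 0 and an undefined result, or, if software skips the zero, statistics based on fewer patients than the n displayed. That conclusion follows from the definitions alone.

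How often it will happen is unknown. The 10% to 65% range for a cell of about 10 patients rests on assumed per-sample BLQ rates of 1% to 10% and independence between patients. The differences between remedies come from one illustrative sample and show direction and order of size only. Cells without a BLQ value, the other statistics in the list, and all efficacy and safety results are unaffected. It should be corrected because the correction is easy, not because the trial's conclusions depend on it.

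**What to change.** In SAP 11.5, limit the zero rule to the arithmetic statistics, median, minimum and maximum. Add that the geometric mean and geometric SD are computed from quantifiable values only, with the n used shown next to the BLQ count. State whether the CV is arithmetic or geometric; if geometric, it follows the same rule. As a tidy-up, add the arithmetic mean to the PK list so that it matches SAP 11.

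The cost is one or two sentences and trivial programming. There is a statistical price: the geometric mean then describes quantifiable samples only and is too high as a summary of all samples. In the illustration with an assumed LLOQ of 1.0, the geometric mean over all ten samples must lie below 24.4^0.9 × 1.0^0.1 = 17.7, while exclusion gives 24.4. The BLQ count therefore has to sit beside it.

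LLOQ/2 substitution is an acceptable alternative. It keeps every sample, but the result depends on the LLOQ and the geometric SD can be inflated, as the table shows. Either will do, provided one rule is chosen and written down before unblinding.
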